### **Early Stopping Criteria**

The Study Director can decide to stop the test day early if they believe this is in the best interests of the trial subjects, study data or both. Data from uncompleted test days will be included in the final

report, but will not be included in final calculations unless this can be justified. The reason for stopping the test day must be recorded, and the sponsor informed within 24 hours.

The most likely reason for stopping the test day is anticipated to be insufficient landing pressure on controls. In this case the efficacy of the repellent cannot be demonstrated, and subjects would be exposed to landing mosquitos unnecessarily. Low landing pressure is defined as fewer than 5 landings on either of the two controls in a 5 minute exposure period. If there are 4 non-consecutive exposure periods with low-landing pressure the test day should be stopped. If there are 3 consecutive exposure periods with low-landing pressure the test day should be stopped.

Mosquitos are unlikely to fly in bad weather, and it is unpleasant for the subjects to be exposed to, so exposure periods will be skipped if wind speed exceeds 16 kph/10 mph, or if it is raining. If there are 4 non-consecutive exposure periods missed due to bad weather the test day should be stopped. If 3 consecutive periods are missed due to bad weather then the test day should be stopped.

If a single landing on a test subject during an exposure period is followed by a missed exposure period (due bad weather) then the first landing will be treated as a confirmed landing. If a confirmed landing occurs during an exposure preceded by a period of low landings or by a missed exposure period due to bad weather, then CPT will be recorded as the earliest time point in that preceding period.

Subjects will be instructed to wash their treated limb as soon as possible after their participation ends and will be provided soap, water, and paper towels at the field site or at the Test Facility where they will be returning to at the end of the testing day.

## **6.8. Environmental Monitoring**

Weather conditions (temperature, relative humidity, cloud cover, precipitation, light intensity, and wind speed) will be recorded at the start and end of the study day. Temperature and wind speed will additionally be recorded for each half hour test period.

## **6.9. Follow-up**

Subjects will be followed up within 24-72 hours after any exposure to mosquitos or test product to assess any possible adverse events. Subjects will also be asked about COVID-19 symptoms and diagnoses. Three attempts will be made to contact the subject. Initial contact will be by email, second and third contacts will be by phone and email. If it is still not possible to contact the subject, then a protocol deviation will be submitted to the IRB.

Alternate contact information will be gathered for each subject for someone who can reach the study participant if contact tracing is necessary. If any subject reports COVID-19, a contact tracing protocol will be followed so that staff and other subjects others potentially exposed to SARS-CoV-2 can be contacted.

In the event that a mosquito captured during testing is found to carry an arbovirus, the Study Director will contact the subjects testing that day. Contact will be made via telephone.

## 7. Statistics and Data Analysis

### 7.1. Sample Size Calculation

EPA statisticians used a Weibull distribution to simulate the sample size required to estimate the median CPT to a given degree of precision. A power analysis of these outputs resulted in a sample size of 13 subjects being chosen. This number allows for over 90% power at a range of expected median CPTs from 2-8 hours (Appendix 4: Sample size calculation).

This sample size is appropriate to achieve at least 90% power that the ratio of 95% LCL mCPT/mCPT  $\geq$  0.6), given that the P5MR (i.e., CPT5th percentile/mCPT) is assumed to be equal or greater than 0.5. The assumption for the variation of CPT data distribution is characterized by the value of P5MR, associated with the selected sample size and the result of power. The P5MR value characterizes the spread of the CPT data distribution. For two products with same mCPT, the product with lower value of P5MR has a wider range of CPT data.

To maintain gender balance among the volunteers, at least 6 volunteers of each sex will be recruited to test each product. An additional 2 subjects will be required to act as untreated controls. Five alternate subjects will be invited to take part in each study day. Subjects will be able to take part in one or both test days. Therefore, a minimum of 20, and a maximum of 40 subjects will be required to complete the trial.

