## Study Synopsis

Sponsor:	Livful Inc.
Study Title:	Field Evaluation of two topically applied insect repellent products containing IR3535 against mosquitos in Louisiana.
Short Title:	Louisiana Mosquito Field Trial 1215
ARCTEC Ref:	1215
LSU IRB Approval Date:	
Study Director:	[name]
Test Facility Manager	[name]
Quality Assurance:	Compliance Services International
Monitor:	[name], ARCTEC, LSHTM, [name]
Objective:	To determine the efficacy and duration of protection of two topically applied insect repellent products at preventing landing by mosquitos. The study will follow the EPA Product Performance Test Guidelines  . It is intended to test the products against natural populations of mosquito species of public health importance within the genera Aedes , Anopheles , and Culex , and to replace data from one site previously tested in Florida with data from a site in Louisiana with adequate landing pressure from target mosquito species of public health relevance.
Study Design / Methodology:	A single-site field setting study using healthy volunteers to test two insect repellent product formulations (lotion, and wipe) against mosquitos.  Subjects will have repellent applied to one lower limb at a standardised dose rate to account for skin area. They will then expose this area only in a field site where mosquitos are recorded landing at a rate of 5 mosquitos per 5 minute or higher. The exposure period will last five minutes and all mosquitos landing on the exposed skin will be collected using an aspirator. 5 minute exposure periods will be repeated every half hour for 14 hours for the lotion and 13 hours for the wipe, or until median CPT can be established by more than half of subjects reaching treatment failure.
Number of Subjects:	Based on power analysis, a sample size of 13 test subjects for each product in this study design would provide sufficient power (>0.90) to obtain a ratio of the lower limit of 95% CI of the estimated median CPT / estimated median CPT is $\geq 0.6$ , where the ratio of the lower limit of 95% CI of the estimated median

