### Human Landing Catches

Human landing collections will start 2 hours after product application. Other products registered with the EPA that contain 20% IR3535, have been shown to give a similar level of protection to 10% DEET. In addition, these test products were previously tested in field sites in Florida, and the EPA allowed data from those studies to support a claim of 3 hours complete protection. Therefore, it is highly unlikely the test products will fail within this time delay. The 2-hour time delay will allow repellent application to be carried out at the test facility where measuring equipment can be kept calibrated and in good condition, before travelling to the field site to start collections.

A minimum of three consecutive exposure periods should occur before subjects experience a first confirmed landing. If a first confirmed landing occurs within the first three exposure periods, the CPT will be counted as 0 hours. Subjects experiencing a first confirmed landing at two hours post application or within the first three consecutive exposure periods should not be replaced.

The mosquito landing pressure will be determined before the treated volunteers expose their legs. Control subjects will expose their lower leg for 5 minutes or until 5 landings occur, whichever is sooner. As soon as 5 landings occur, regardless of whether 5 minutes have elapsed, the control subject can cover the lower leg to minimize the potential for mosquito bites. Landing pressure will be assessed for each 30 minute interval. The time of the landings and when the threshold number of landings occur will be recorded. If the landing pressure is insufficient, test subjects will carry out their exposures in that time period unless the total number of exposure periods with low landing pressure exceeds three consecutive periods or four non-consecutive periods with inadequate landings on controls, and the test should be stopped.

The treated lower limb of the test subjects will be exposed for 5 consecutive minutes, during each 30 minute interval for the trial period. Under supervision of a trained member of staff or another subject, the number and timing of each landing during each exposure period for each subject will be recorded.

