### 7.2. Statistical Methods

The endpoint for Complete Protection Time will be time to treatment failure for each subject test. Treatment failure is the time at which the product no longer provides complete protection, which is determined as the time at which the first confirmed landing occurred. First confirmed landing is a landing that is followed by another landing within a 5-minute exposure period, or a landing in an exposure period immediately followed by an exposure period in which a landing occurred. The times to treatment failure will be analyzed using Kaplan-Meier Survival functions, and from these the median Complete Protection Time and 95% confidence intervals (CI) will be calculated. The 95% CI of the estimated mCPT will be calculated with the log-log transformation applied to survival function and Kaplan-Meier survival curves will be presented in the study report.

A first confirmed landing occurring within the first 3 consecutive exposure periods will be considered as 0 for statistical purposes.

Participants that withdraw before the start of testing will be replaced with alternates. Participants that withdraw during the test day will have their data included in the statistical analysis as right censored data. Right-censored data are those data that, despite monitoring of the outcome event, the event does not occur within the study duration or because the participant has withdrawn. Withdrawn subjects whose data are right censored should not be replaced. If 3 or more participants on an individual test day withdraw before they record treatment failure, the Study Director will make the decision as to whether to continue testing and include these right-censored values in the analysis, or end the test day, and attempt a repeat at a later date. In this case the data will be reported, but not included in statistical analysis. The decision, and reasons to continue or discontinue testing, will be recorded.

Adverse events will be tabulated and included in the study report. Adverse events occurring after the end of subject participation but before the end of the study will be listed separately.

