## 11.4. Appendix 4: Sample Size Calculation

### Objective

To determine the sample size N such that the proposed IR3535 mosquito repellency study has sufficient power to obtain a given degree of **precision** in the estimate of Median Complete Protection Time (mCPT). This precision – designated as “K” -- will be expressed by 95% LCLmCPT/estimated mCPT

The simulation used to estimate varying sample sizes will require that that 95% LCLmCPT/estimated mCPT < K, given the true **variation** of the Complete Protection Time (CPT) distribution, expressed by a the Weibull distribution family and a parameter, P5MR, defined as the 5th percentile/mCPT.

**Additional Details:** Two important considerations in developing an estimate of the CPT as a measure of repellency are the **precision** of the estimate and the **variability** of CPT in the population. The precision of the estimate -- designated as “K” -- is defined here as follows:

$$K = 95\% \text{ LCL}_{\text{mCPT}} / \text{estimated mCPT}$$

Where: mCPT= median protection time

95% LCLmCPT = 95% lower confidence limit on mCPT

The degree of variation of the mCPT distribution will be defined as the P5MR which is defined here as the ratio between the mCPT of the 5th percentile of the population to the Median CPT (mCPT) of the population:

$$\text{P5MR} = \text{CPT}_{5^{\text{th}} \text{ \%ile}} / \text{mCPT}$$

Where:

mCPT= median protection time

CPT5th %ile = 5th percentile of the distribution of CPT

The simulation performed by EPA estimates the power of a mosquito repellency study design as a function of the following parameters:

- Sample size
- (Required) precision K of estimated mCPT
- mCPT
- P5MR

Table 1 below presents the power estimates from simulations in which the data were randomly generated from Weibull distributions for K = 0.6. These are shown for various values of mCPT (ranging from 2 to 8 hours), P5MR (ranging from 0.2 to 0.8), and Sample Size (ranging from 10 to 20). Note that K reflects the precision of the estimate of mCPT. For example, the K value of 0.6 requires that the 95% LCL on a median protection of 10 hours be no less than 6 hours while a K value of 0.8 requires that the

95% LCL on that same median protection time be no less than 8 hours. The K of 0.8, then, requires a more precise estimate of the MPT than a K of 0.6.

Full tables and graphs of the simulations are available in trial files.

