**Table 1: Results of power analysis when the lowest acceptable ratio 95% LCL/mCPT = 0.6 (Weibull distribution)**

Median (hours)	P5MR	Sample size										
		_10	_11	_12	_13	_14	_15	_16	_17	_18	_19	_20
2	0.2	0.071	0.291	0.207	0.473	0.362	0.369	0.502	0.494	0.637	0.626	0.521
	0.4	0.297	0.691	0.594	0.841	0.804	0.779	0.893	0.898	0.939	0.945	0.932
	0.5	0.498	0.850	0.802	0.942	0.938	0.921	0.968	0.977	0.964	0.982	0.986
	0.6	0.733	0.949	0.943	0.962	0.971	0.955	0.954	0.979	0.915	0.951	0.971
	0.7	0.893	0.945	0.955	0.875	0.918	0.852	0.855	0.893	0.810	0.859	0.886
	0.8	0.819	0.786	0.826	0.666	0.734	0.591	0.637	0.708	0.558	0.632	0.689
4	0.2	0.043	0.208	0.146	0.356	0.289	0.254	0.432	0.380	0.567	0.516	0.435
	0.4	0.241	0.595	0.521	0.783	0.737	0.709	0.849	0.842	0.930	0.920	0.884
	0.5	0.412	0.795	0.730	0.921	0.901	0.888	0.956	0.964	0.986	0.988	0.973
	0.6	0.648	0.938	0.899	0.987	0.980	0.976	0.995	0.997	0.997	0.999	0.998
	0.7	0.869	0.988	0.986	0.993	0.995	0.994	0.992	0.998	0.977	0.992	0.996
	0.8	0.975	0.982	0.987	0.948	0.970	0.949	0.934	0.968	0.887	0.932	0.954
6	0.2	0.075	0.204	0.153	0.339	0.280	0.252	0.426	0.369	0.557	0.490	0.424
	0.4	0.227	0.572	0.504	0.759	0.743	0.689	0.851	0.826	0.929	0.916	0.885
	0.5	0.408	0.779	0.729	0.914	0.905	0.873	0.963	0.958	0.987	0.981	0.978
	0.6	0.645	0.925	0.906	0.984	0.980	0.977	0.997	0.997	1.000	0.999	0.999
	0.7	0.874	0.990	0.988	0.998	0.999	0.999	1.000	1.000	0.999	1.000	1.000
	0.8	0.986	0.998	0.999	0.993	0.995	0.994	0.990	0.997	0.975	0.989	0.995
8	0.2	0.323	0.346	0.362	0.457	0.443	0.361	0.537	0.453	0.636	0.564	0.522
	0.4	0.314	0.586	0.552	0.769	0.753	0.700	0.858	0.836	0.934	0.919	0.891
	0.5	0.421	0.779	0.732	0.914	0.904	0.875	0.960	0.956	0.989	0.985	0.979
	0.6	0.638	0.927	0.906	0.983	0.979	0.974	0.997	0.997	1.000	0.999	1.000
	0.7	0.874	0.990	0.989	0.999	1.000	0.999	1.000	1.000	1.000	1.000	1.000
	0.8	0.985	0.999	1.000	0.997	1.000	0.999	0.998	1.000	0.994	0.998	0.999

NOTE: Yellow indicates power > 0.8; orange indicates power > 0.9 blue indicates unusual power when median complete protection time = 2 hours and P5MR = 0.8.

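### The stated power of over 90% for median CPTs of 2-8 h ignores the 0 h coding of early failures; at P5MR 0.5 it is 0.47 at a 4 h median and reaches 0.90 only from about 5.5 h

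*Protocol*

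**What the plan says.** Section 7.1 reports that "A power analysis of these outputs resulted in a sample size of 13 subjects being chosen", and adds: "This number allows for over 90% power at a range of expected median CPTs from 2-8 hours". The criterion is a ratio of the lower 95% limit to the estimated median CPT of at least 0.6, and P5MR (5th percentile over median) is assumed to be 0.5 or more. The Study Synopsis makes the same claim for this design, with no condition on the median or on P5MR: "a sample size of 13 test subjects for each product in this study design would provide sufficient power (>0.90").

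Appendix 4 says that "the data were randomly generated from Weibull distributions for K = 0.6". It lists sample size, K, median CPT and P5MR as the parameters. For n=13 and P5MR 0.5, its Table 1 gives 0.942, 0.921, 0.914 and 0.914 at medians of 2, 4, 6 and 8 h.

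The conduct and analysis rules are elsewhere. Section 6.7 (Human Landing Catches) says "Human landing collections will start 2 hours after product application", with one exposure per half hour, and "If a first confirmed landing occurs within the first three exposure periods, the CPT will be counted as 0 hours". Section 7.2 repeats the rule for the analysis: "A first confirmed landing occurring within the first 3 consecutive exposure periods will be considered as 0 for statistical purposes". It also specifies Kaplan-Meier estimation with a log-log 95% interval for the median.

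**The concern.** The first three exposures fall at 2.0, 2.5 and 3.0 h, so every failure up to 3 h enters the analysis as 0 h. That cut-off lies inside the 2-8 h range for which power is claimed. Zeros among the smallest CPTs pull the lower limit to 0, and no positive median then meets a ratio of 0.6. Appendix 4 mentions neither the delayed start nor the coding, so its figures appear to describe a different analysis from the planned one.

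The power statement is the only justification given for 13 subjects. If it fails in part of its range, a trial of a product in that range may report a lower limit of 0 h where the protocol promised a tight one.

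**Working it through.** **Inputs.** n=13, K=0.6, Weibull CPTs, P5MR of 0.5 or more (Section 7.1, Appendix 4); log-log Kaplan-Meier limits (Section 7.2); first exposure at 2 h, then every 0.5 h, failures at 3.0 h or earlier coded 0 (Sections 6.7, 7.2).

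**Step 1: which order statistic is the lower limit?** With d failures, no earlier censoring, S = (13−d)/13 and Greenwood term V = d/[13(13−d)], the lower log-log bound is S^exp(1.96·√V/|ln S|).
- d=2: S = 0.846, V = 2/143 = 0.01399, bound = 0.512.
- d=3: S = 0.769, V = 3/130 = 0.02308, bound = 0.442.

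The bound first falls below 0.5 at the third failure, so the lower limit is the 3rd ordered CPT. The median is the 7th. Stopping once more than half have failed affects neither.

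**Step 2: reproduce the plan's figures.** Weibull shape = ln[ln(1/0.95)/ln 2]/ln(P5MR), which is 3.756, 5.097, 7.300 and 11.668 for P5MR 0.5, 0.6, 0.7 and 0.8. At P5MR 0.5 without the 0 h coding, simulated power is:

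| Median | Continuous times | Failure recorded at next half hour | Table 1 |
|---|---|---|---|
| 4 h | 0.904 | 0.938 | 0.921 |
| 6 h | 0.904 | 0.924 | 0.914 |
| 8 h | 0.904 | 0.923 | 0.914 |

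The two recording rules bracket Table 1. At 2 h they also bracket it, more widely (0.904 and 0.977 against 0.942). Table 1 is therefore consistent with a simulation that has no 0 h coding. Its 2 h value could not arise with the coding, because about 96% of CPTs would then be 0.

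**Step 3: a bound without a Weibull assumption.** At a true median of 3 h each subject has probability 0.5 of failing by 3 h. P(at least 3 of 13) = 1 − (1+13+78)/8192 = 0.989. The lower limit is then 0, so power is at most about 0.01 whatever the P5MR.

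**Step 4: exact check at a 4 h median, P5MR 0.5.** F(3 h) = 1 − 0.5^[(3/4)^3.756] = 0.2096. P(at least 3 of 13) = 0.533. The lower limit is 0 in 53% of trials, so power cannot exceed 0.467.

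**Step 5: full simulation under the planned rules** (100,000-200,000 trials per cell, failure recorded at the next half-hourly exposure from 2 h). At P5MR 0.5:

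| Median (h) | 3 | 3.5 | 4 | 4.5 | 5 | 5.5 | 6 | 8 |
|---|---|---|---|---|---|---|---|---|
| Power | 0.01 | 0.16 | 0.47 | 0.73 | 0.86 | 0.90 | 0.92 | 0.92 |
| Table 1 | – | – | 0.921 | – | – | – | 0.914 | 0.914 |

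At a 4 h median, power by P5MR is 0.47 (0.5), 0.70 (0.6; Table 1 0.987), 0.92 (0.7; Table 1 0.993) and 0.997 (0.8). Power first reaches 0.90 at a median of about 5.5, 4.5, 4.0 and 3.6 h for P5MR 0.5, 0.6, 0.7 and 0.8. A cut at 13 or 14 h changes these figures by no more than 0.001.

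**Step 6: the text against its own table.** At n=13 and a 2 h median, Table 1 gives 0.875 for P5MR 0.7 and 0.666 for P5MR 0.8. Both cells meet the stated P5MR condition and lie below 0.90. The table note flags only one of them: "blue indicates unusual power when median complete protection time = 2 hours and P5MR = 0.8".

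**The case against.** **The products may last longer.** Testing runs to 14 h for the lotion and 13 h for the wipe, and Section 6.7 regards failure during the 2 h delay as very unlikely. If the true medians are about 6 h or more, the stated power holds. This stands as a limit on the consequence. But the protocol gives no expected median. Its one figure for these products is a 3 h protection claim allowed from the Florida data, which is not a median and does not rule out the lower range.

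**P5MR 0.5 is the edge of the assumption.** At a 4 h median the claim survives for P5MR 0.7 and above. However, 0.5 is the boundary the protocol chose, and at 2-3 h no P5MR rescues it.

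**The 2 h start is not itself the cause.** Correct: with the start delay alone, power at 4 h stays at 0.939. The loss comes from the 0 h coding, and the start matters because it places the cut-off at 3 h.

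**The coding is deliberate and conservative.** Agreed. A lower limit of 0 after three early failures is that rule working as intended. The fault is in the power sentence, not in the rule.

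**The thresholds depend on how failure times are gridded.** This also stands. At P5MR 0.5, power at 5.5 h is 0.89 with continuous times and 0.85 with rounding to the nearest half hour, and 0.90 is reached near 6 h and 6.5 h. At a 4 h median, rounding gives 0.27 and rounding down 0.12, so 0.47 is not an overstatement of the problem. The back-dating of CPT after low-landing or missed periods (Section 6.7, Early Stopping Criteria) was not modelled. It moves CPTs earlier, so at the 3 h cut-off it can only add zeros.

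**Conclusion.** The concern holds. Under the protocol's own rules, 13 subjects do not give over 90% power across medians of 2-8 h. At P5MR 0.5 the claim fails below about 5.5 h, and at 4 h the trial is more likely than not (0.53) to report a lower limit of 0 h. At 3 h power is about 0.01 for any P5MR, and at 2 h the criterion cannot be evaluated. From about 6 h the coding has almost no effect.

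The result for 3 h rests only on the log-log interval and the coding rule. The other figures assume Weibull CPTs, no censoring before the median, and failure recorded at the next half-hourly exposure. The contradiction with Table 1 at 2 h needs no assumption. This should be fixed, but it is an error in the stated justification and does not by itself show that 13 subjects are too few.

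**What to change.** Keep the 0 h coding as the primary rule. Observed times should not replace it, because a failure seen at the first exposure could have occurred at any time from 0 to 2 h.

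Re-run the Appendix 4 simulation with the 2 h start, the half-hourly grid, the first three periods coded 0 and the 13 h and 14 h cuts, and state the gridding rule. Then restate the covered range by P5MR in the Synopsis, Section 7.1 and Appendix 4. If the re-run confirms the figures above, the text could read:

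> Allowing for the 2 h start and the coding of failures in the first three periods as 0 h, 13 subjects give at least 90% power to meet the 0.6 criterion for median CPTs from about 5.5 h at P5MR 0.5, 4.5 h at 0.6, 4.0 h at 0.7 and 3.6 h at 0.8. Power is lower at shorter medians, and the ratio is undefined when the estimated median is 0.

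The thresholds should come from the re-run, since another gridding rule would move them upwards. The cost is one simulation and wording in three places. The stated range becomes narrower; subject numbers, conduct and primary coding do not change.

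### Section 7.1 claims over 90% power at n=13 for medians of 2-8 h and P5MR of 0.5 or more, but its own power table shows 0.875 and 0.666 in two cells at a 2 h median

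*Protocol*

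**What the plan says.** Section 7.1 reports that "A power analysis of these outputs resulted in a sample size of 13 subjects being chosen". Two statements about power follow. The first refers to Appendix 4: "This number allows for over 90% power at a range of expected median CPTs from 2-8 hours". The second names the precision criterion, a ratio of lower limit to median of at least 0.6, and a condition on spread: "This sample size is appropriate to achieve at least 90% power that the ratio of 95% LCL mCPT/mCPT" meets that bound, "given that the P5MR (i.e., CPT5th percentile/mCPT) is assumed to be equal or greater than 0.5". Neither sentence sets an upper limit on P5MR or makes an exception for any median.

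Appendix 4 says the simulations cover "various values of mCPT (ranging from 2 to 8 hours), P5MR (ranging from 0.2 to 0.8), and Sample Size (ranging from 10 to 20". Its Table 1 carries a colour key, one item of which reads "blue indicates unusual power when median complete protection time = 2 hours and P5MR = 0.8". The key says nothing about P5MR 0.7, and section 7.1 does not carry the remark over.

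The synopsis gives power above 0.90 for 13 subjects and the 0.6 criterion, but names no range of medians or P5MR.

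**The concern.** Read together, the two sentences in 7.1 treat P5MR 0.5 as the worst case and promise 90% for anything tighter, at every median from 2 to 8 h. That holds only if power does not fall back below 0.90 as P5MR rises. In the 2 h block of Table 1 it does: at n=13 it goes from 0.942 to 0.962, then to 0.875 and 0.666.

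What is at stake is the accuracy of the stated justification. Table 1 is the only support shown for n=13, and section 4.1 says the EPA and the HSRB review the protocol before recruitment starts. A reader of one column can see that the sentence is not true over the range it names.

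**Working it through.** **Inputs**
- n = 13 per product, power of at least 0.90, P5MR of 0.5 or more, medians 2-8 h: section 7.1.
- Success criterion K = lower 95% limit / estimated median of at least 0.6: section 7.1 and Appendix 4.
- Power values: Appendix 4, Table 1, column for n=13. The tabulated P5MR values that satisfy the condition are 0.5, 0.6, 0.7 and 0.8.

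**1. The plan's own figure.** At P5MR 0.5:

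| Median | n=10 | n=11 | n=12 | n=13 |
|---|---|---|---|---|
| 2 h | 0.498 | 0.850 | 0.802 | 0.942 |
| 4 h | 0.412 | 0.795 | 0.730 | 0.921 |
| 6 h | 0.408 | 0.779 | 0.729 | 0.914 |
| 8 h | 0.421 | 0.779 | 0.732 | 0.914 |

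The lowest value at n=13 is 0.914. Thirteen is the smallest tabulated size above 0.90 at all four medians, so the choice of n reproduces.

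**2. The whole range claimed.** n=13, P5MR of 0.5 or more:

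| Median | 0.5 | 0.6 | 0.7 | 0.8 |
|---|---|---|---|---|
| 2 h | 0.942 | 0.962 | **0.875** | **0.666** |
| 4 h | 0.921 | 0.987 | 0.993 | 0.948 |
| 6 h | 0.914 | 0.984 | 0.998 | 0.993 |
| 8 h | 0.914 | 0.983 | 0.999 | 0.997 |

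- Cells covered: 4 medians × 4 P5MR values = 16.
- At or above 0.90: 14, the lowest being 0.914.
- Below 0.90: 2. Shortfalls are 0.900 − 0.875 = 0.025 and 0.900 − 0.666 = 0.234.

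**3. Would more subjects mend the two cells?** At n=20 the table gives 0.886 (P5MR 0.7) and 0.689 (P5MR 0.8). The P5MR 0.8 row at 2 h never reaches 0.90 for any n from 10 to 20; its highest value is 0.826, at n=12. The P5MR 0.7 row passes 0.90 only at n=11, 12 and 14 (0.945, 0.955, 0.918). This is not the pattern of a sample that is simply too small.

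**4. Can the cause be established?** Weibull data were re-simulated at n=13 with shape k = ln(ln 2 / −ln 0.95) / ln(1/P5MR) and scale = median / (ln 2)^(1/k). The limit was the Kaplan-Meier log-log limit named in section 7.2 ("The 95% CI of the estimated mCPT will be calculated with the log-log transformation applied to survival function"). At a 2 h median:
- With continuous times, power was 0.999 (P5MR 0.7) and 1.000 (P5MR 0.8).
- With times on half-hour grids, results ran from 0.732 to 0.997 (P5MR 0.7) and from 0.258 to 0.990 (P5MR 0.8), depending on the rounding and on the rule for reading the lower limit.
- With times rounded to the nearest half hour and the limit read from the lower confidence curve, one coding gave 0.685 at P5MR 0.8, with no limit in 31.5% of runs. Another found a limit in every run and gave at least 0.98.

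No variant matched both printed cells. Appendix 4 states neither a time grid nor a rule for the limit, so tied times are a plausible cause but not a demonstrated one.

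**The case against.** Three arguments against giving this much weight are sound.

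- **A 2 h median is barely observable here.** Section 6.7 starts collections 2 h after application and scores a first confirmed landing in the first three exposure periods as 0. Appendix 3 places those periods at 2, 2.5 and 3 h. Leaving aside the back-dating rule for low-pressure or skipped periods, a recorded failure is therefore either 0 or at least 3.5 h. With P5MR of 0.7-0.8 and a 2 h median, the 5th percentile would be 1.4-1.6 h, before any exposure takes place. At medians of 4, 6 and 8 h all 12 cells meet 0.90. This limits the practical effect, but 7.1 itself extends the claim down to 2 h.
- **The larger anomaly is disclosed.** The key to Table 1 marks the 0.666 cell as unusual, and 7.1 refers to that appendix. But the key leaves out the 0.875 cell, and the text still claims the full range.
- **The synopsis is not contradicted in the same way.** It names no range of medians or P5MR, so it cannot be called false over a range.

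A reader might also infer more than the documents support:
- That 13 subjects are too few. Steps 1 and 3 show otherwise.
- That power generally falls as the data become tighter. At 2 h it first rises, and at 6 and 8 h the drop from P5MR 0.7 to 0.8 is only 0.005 and 0.002.
- That the lower limit cannot be estimated at a 2 h median. That depends on a grid and a rule which the protocol does not give.

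**Conclusion.** The point holds as a correction to a stated figure. Two of the 16 cells covered by section 7.1 are below 0.90 at n=13: 0.875 and 0.666, both at a 2 h median, with P5MR 0.7 and 0.8. The other 14 are at least 0.914. The finding rests on reading the printed table and on taking the two sentences of 7.1 together; it needs no simulation.

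The sample size stands. The case that determines it, P5MR 0.5, is supported at every tabulated median, and no decision on design or analysis changes. Why the two cells are low remains open.

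**What to change.** Replace the power claim in section 7.1 with wording to this effect:

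> *With 13 subjects, Appendix 4 Table 1 gives power of at least 0.90 for a ratio of 0.6 at the tabulated medians of 4, 6 and 8 h with P5MR between 0.5 and 0.8. At a median of 2 h it does so for P5MR 0.5 and 0.6 only; the tabulated power there is 0.875 at P5MR 0.7 and 0.666 at P5MR 0.8.*

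This also gives the P5MR condition an upper bound, since the table stops at 0.8. A cross-reference from the synopsis to 7.1 is optional. Appendix 4 says the full simulation output is in the trial files; an explanation of the two cells should be added only if those files confirm it.

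The cost is a sentence or two and a slightly less favourable statement of power. Sample size, conduct and analysis are unchanged.
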